1.0 Objectives

- 1.0 Establish the safety and efficacy of using stereotactic body radiotherapy (SBRT) to treat spine and para-spinal tumors in a single session.
- 1.1 Document frequency and severity of pain, symptoms and symptom interference, as well as quality of life before and after treatment.
- 1.2 Document changes in neurological function at defined intervals compared to pre-treatment neurological function

2.0 Background

Each year, approximately 200,000 cancer patients develop vertebral metastases [Schabert 1985]. Palliative treatment of bone metastases comprises a significant portion of cancer care in that a large proportion of that expenditure is spent on palliation of painful osseous metastases. Radiation therapy can be highly effective in relieving painful bone metastases given that almost 90% of patients will experience improvement in their pain, with complete pain relief in about half of treated patients (Janjan 1997). Unlike curative therapy which uses a high total dose of radiation to achieve tumor control, palliative therapy generally uses a lower total dose of radiation given over a shortened hypofractionated schedule.

A large collective experience has been described by the Radiation Therapy Oncology Group (RTOG) for bone metastases. The RTOG study concluded that low-dose, short-course treatment schedules were as effective as high-dose protracted treatment programs. For solitary bone metastases, there was no difference in relief of pain when 20Gy using 4 Gy fractions was compared to 40.5 Gy in 2.5Gy per fraction. In multiple bone metastases, 30Gy using 3Gy fractions was compared with 15 Gy using 3 Gy fractions, 20Gy using 4 Gy fractions and 25 Gy using 5 Gy fractions (Tong 1982). No differences were seen in the rate of pain relief between these treatment schedules. Partial relief of pain was achieved in 83% and complete relief occurred in 53% of patients. Multiple other studies have published benefits of hypofractionated radiation therapy for the treatment of bone metastases (Gaze 1997, Hoskin 1992, Jeremic 1998, Madsen 1983, Niewald 1996) and even in the face of spinal cord compression (Maranzano 1997). There are studies to support the effectiveness of single fractions of radiotherapy for bone metastases (Nielson 1999, 1998, Steenland 1999). The RTOG 97-14 study addressed the palliation of symptoms and quality of life for patients with osseous metastases by comparing 3 Gy x 10 fractions to 8 Gy x 1 fraction in a randomized trial involving 897 eligible patients with breast or prostate cancer and painful bone metastases. The complete response and partial response for pain for patients who received 8 Gy was 15% and 50%, compared to 18% and 48% for patients who received 30 Gy. In the preliminary report from this trial, it was concluded that palliative external beam radiation therapy is very effective in providing pain relief and that pain and narcotic relief is equivalent for both 30 Gy in 10 fractions and 8 Gy in a single fraction (Hartsell 2003).

While conventional radiation treatment is used to provide palliation for the vast majority of patients with spinal metastasis, there are at least 3 drawbacks. First, conventional irradiation is limited by the dose that can be tolerated by the spinal cord which may limit its ability to control disease. Second, excessive amounts of normal tissue are irradiated. Third, conventional irradiation is relatively inconvenient since most treatment courses last about 2 weeks.

In our experience from protocol ID02-446 which is evaluating SBRT given in 3 - 5 fractions for spinal metastases, patients find the option of non-invasive SBRT to the spine to be attractive when clinically indicated. However, the ability to give this treatment in a single fraction would be desirable if it could be done safely. This perception is confirmed by a study from Canada on 101 patients in which most participating patients indicated that an 8 Gy-in-one fraction regimen was favored, over a 2 week course of radiation treatment independent of the treated site. The convenience of the treatment plan and the likelihood of bone fracture were the most important factors influencing patients' choice (Szumacher 2005).

Stereotactic radiosurgery has been originally applied only to the brain. It is a routine procedure that delivers a single clinically significant focused dose of radiation into the tumor while delivering a clinically insignificant dose of radiation to the surrounding brain. The value of stereotactic radiosurgery in the brain has been established by numerous published reports (Auchter 1996). The linear accelerator (LINAC) based stereotactic radiosurgery program at U.T. M.D. Anderson Cancer Center was started in 1991 as a joint collaboration between the Departments of Neurosurgery, Radiation Oncology, and Radiation Physics. The program has been successful in treating patients afflicted with metastatic brain disease and has grown considerably since its inception. In the Fall of 1999, a dedicated stereotactic unit was installed that would be able to significantly improve the ability to handle the increasing number of referrals for stereotactic radiosurgery. Over 200 patients are now treated routinely at MD Anderson Cancer Center on an annual basis with minimal degree of invasiveness and minimal complication rates of less than 1%.

Stereotactic body radiotherapy (SBRT) is based on radiosurgical principles applied to targets outside the head. In contrast to the brain which is an ideal model because it is rigidly contained within the bony confines of the skull, extracranial targets in the body do not afford the same luxury of immobilization. Stereotactic radiosurgery to extra-cranial sites has been hampered by difficulties with creating a robust system that produces highly reproducible body-immobilization. Preliminary experience with SBRT to the spine is summarized: Investigators at the University of Arizona reported on a prototype for stereotactic radiosurgery to the spine in 5 patients whose tumors that had failed to respond to spinal cord tolerance doses delivered by conventional radiation therapy to a median dose of 45Gy. Tumors were treated with single-fraction stereotactic radiosurgery with a median single fraction dose of 10Gy (range, 8-10 Gy). A short median follow-up of 6 months revealed no radiographic or clinical progression of the treated tumor in any patient. In 3 patients, there was CT or MRI documented regression of the treated tumor. A single complication of esophagitis occurred involving C6-T1 that resolved with medical therapy. Although the follow-up is short, all patients received significant palliation of pain (Hamilton 1996). An update to this series was reported on 9 patients presenting with recurrent disease to the spinal column. All patients had failed standard therapy consisting of surgery, external fractionated radiation therapy, and /or chemotherapy. Six of 9 patients had epidural compression, and 4 of the 9 had evidence of myelopathy. Two of 9 patients had radicular symptoms secondary to compression from the tumor. Patients were treated with

median radiosurgical dose of 8Gy (range 8-10 Gy), yet median dose delivered to the already prior irradiated spinal cord was 1.79 Gy. Three minor complications were reported including radiation-induced esophagitis, wound infection and one patient requiring an additional 24 hour hospitalization. No instances of radiation myelitis or neurological deterioration were observed. This phase I study demonstrated technical feasibility of spinal radiosurgery for the control of metastases to the vertebral column even in the face of epidural compression (Hamilton 1995).

Bilsky et al from Memorial-Sloan-Kettering Cancer Center, described preliminary experience in which intensity modulated radiation therapy (IMRT) was used to treat paraspinal lesions in patients who harbor locally recurrent tumors. The tumor received 20Gy in four fractions with 100% isodose to the tumor and 20% to the spinal cord. One year after IMRT, the tumor was well controlled with significant pain relief and there was no known evidence of radiation myelopathy (Bilsky 2001).

Murphy et al describe a new method for treating metastatic spinal tumors in which non-invasive image-guided frameless stereotactic radiosurgery is performed (Murphy 2001). The authors developed a system that coupled an orthogonal pair of x-ray cameras to a dynamically manipulated robot-mounted linear accelerator that guides the radiation beam to treatment sites associated with radiographic landmarks. Alignment of the treatment dose with the target volume was accurate to within 1.5mm. Four patients underwent spine radiosurgery with total prescription doses of 10 to 16 Gy in one or two fractions. The ability to deliver 16 Gy to the perimeter of an irregular target while limiting cord exposure to below 8 Gy was demonstrated (Murphy 2001).

At the University of Texas M.D. Anderson Cancer Center, a new stereotactic body radiation program to the spine was initiated in collaboration with the Department of Neurosurgery in November of 2002 to treat patients afflicted with spinal or paraspinal metastases. The program utilizes a system involving a Tyco/Radionics extracranial stereotactic body frame and a linear accelerator/“CT-on-Rails” system within in the Department of Radiation Oncology to deliver stereotactic body radiotherapy to the spine in the context of ongoing protocol ID02-446. Conformality to the tumor volume and protection of critical internal structures such as the spinal cord is theoretically assured by determination of treatment position and adjusting for any changes observed in treatment position using CT-on-rails imaging immediately prior to radiation treatment. The distinctiveness of this system is that it allows the patient to be scanned in the same treatment position on the same treatment couch within the same treatment room eliminating the need for transporting the patient to another room with a CT scanner.

The reproducibility of patient setup in our protocol ID02-446 has been published to be able to treat patients with an accuracy within 1mm [Shiu 2003]. The phase I results from our protocol ID02-446 was that the SBRT was safe and feasible to give in 5 fractions [Chang 2004]. Interim results from ID02-446 showing a crude tumor control rate of 87.3%, and no evidence of Grade 3-4 neurological toxicity will be presented at the American Society of Therapeutic Radiation Oncology meeting [Chang 2005]. In our interim analysis of data from ID02-446, we looked at the actuarial 1-year freedom from progression of spinal tumors, and found that the proportion of spinal tumors controlled in renal cell carcinoma patients compared to non-renal cell carcinoma patients was 95% compared to 56% (log-rank p = 0.02). Therefore, in this protocol that treatment plan will be stratified for renal cell carcinoma patients and non-renal cell carcinoma patients such that renal cell carcinoma patients will receive a higher dose, in the hopes of achieving a higher level of tumor control. The results from ID02-446 serve as a precursor and the basis for the proposed study of single session SBRT. This study is designed to establish the safety, and efficacy of single session SBRT for patients with metastatic spine disease.

3.0 Patient Eligibility

Inclusion Criteria:

- 1) Radiographically documented spine or paraspinal metastasis demonstrated on spine MRI within 4 weeks of registration
- 2) Maximum of 2 metastatic sites in the spine to be irradiated in single session
- 3) Informed consent for irradiation of spinal or para-spinal tumor (s)
- 4) Diagnosis of cancer including but not limited to lung (non-small cell and small cell), breast, prostate, renal cell, melanoma, gastrointestinal, and germ cell tumors, unknown primary tumors
- 5) Karnofsky performance status of at least 40 (ie not requiring active hospitalization)

Exclusion Criteria:

- 1) Worsening neurological status due to radiographic evidence of spinal cord compression requiring immediate surgical decompression or emergent conventional external radiation therapy.
- 2) Delay in initiation of radiation treatment would be potentially detrimental to neurological outcome
- 3) Prior irradiation to current site of interest in the spine
- 4) Spinal metastasis in the cervical spine are not eligible for treatment
- 5) Unstable spine requiring surgical stabilization.
- 6) Sites outside the spine (eg. lung, liver) are not eligible for treatment
- 7) Patients currently receiving, or who have received chemotherapy within 30 days are not eligible
- 8) Inability to tolerate lying flat on treatment couch for greater than 30 minutes.
- 9) Patient with multiple myeloma
- 10) Patients unable to undergo MRI of the spine
- 11) Patients with pacemakers

4.0 Treatment Plan

All patients will receive CT image-guided SBRT using intensity modulated radiation therapy to maximize conformality to the tumor while attempting to spare the spinal cord as much as possible. Patients will be stratified into two groups: 1) non-renal cell carcinoma patients 2) renal cell carcinoma patients.

Spinal Metastases

Non-renal cell metastases

For spinal metastases (spinal- thoracic, lumbar, sacral or paravertebral regions) other than renal cell carcinoma, the dose will be prescribed to the mean clinical target volume (CTV) or vertebral body such that 16 Gy will achieve 80-90% coverage of the CTV. The mean gross tumor volume (GTV) will be prescribed to receive 18 Gy with at least 90% coverage of the GTV if possible in a single fraction. Dose reduction may be necessary to respect spinal cord tolerance in the next section.

Renal-cell metastases

For renal cell carcinoma metastasis, the dose will be prescribed to the mean CTV or vertebral body such that 16 Gy will achieve 80-90% coverage of the CTV. The mean gross tumor volume (GTV) will be prescribed to receive 24 Gy with at least 90% coverage of the GTV if possible in a single fraction. Dose reduction may be necessary to respect spinal cord tolerance in the next section.

Paraspinal metastases

Non-renal cell metastases

For paraspinal metastases other than renal cell carcinoma, the dose will be prescribed to the mean GTV such that 18 Gy will achieve 80-90% coverage of GTV if possible in a single fraction. Dose reduction may be necessary to respect spinal cord tolerance in the next section.

Renal cell metastases

For paraspinal metastases arising from renal cell carcinoma, the dose will be prescribed to the mean GTV such that 24 Gy will achieve 80-90% coverage of the GTV if possible in a single fraction. Dose reduction may be necessary to respect spinal cord tolerance in the next section.

Spinal cord dose constraint

Dose to the spinal cord will respect its tolerance such that the dose of the spinal cord will in general be limited to 8 Gy and the spinal cord + 2mm will be less than 12 Gy. No greater than 0.01 cc of spinal cord itself can exceed 10 Gy based on tabular dose volume histogram. Patients who have been previously irradiated to the spine in the same region of interest will not be eligible for this protocol.

5.0 Pretreatment evaluation

- 1) Patients will undergo a history and neurological exam. Neurologic function will be graded from 1 to 4 according to the McCormick classification scheme.
- 2) MRI of the spine must be performed within 1 month of registration.
- 3) A pretreatment CT scan will be obtained for treatment planning.
- 4) The SF-12v2 Health Survey, the M.D. Anderson Symptom Inventory (MDASI) and the Brief Pain Inventory (BPI Short Form), which includes assessment of pain medications will be administered for baseline assessment within 1 week of registration.
- 5) At the time of enrollment, patients will be noted to either have hepatic metastases present or absent.
- 6) Based on the radiation treatment plan, the gross tumor volume (GTV) representing the spinal or paraspinal metastasis, the clinical target volume (CTV) representing the GTV and the entire vertebral body for spinal metastases will be recorded.

6.0 Evaluation During Study

Patients will be evaluated at 1, 2, 3, and 4, and 8 weeks following completion of radiation therapy by telephone, fax, or mail. Patients will be seen for follow up visits at 3, 6, 9, 12, 18, and 24 months and then every six months thereafter; History, neurological exam, and neurologic function according to the McCormick scale will be assessed. MRI of the spine will be obtained at 3, 6, 9, 12, 18, and 24 months and then every six months thereafter. Included in the appendices, the Brief Pain Inventory (BPI) (Short Form), MD Anderson Symptom Inventory (MDASI) and SF-12v2 Health Survey will be administered at each clinic and telephone follow up. Pain medication requirements will be recorded on the BPI.

The BPI is a 17 item patient self rating scale assessing demographic data, use of medications, as well as sensory, and reactive components of pain (5). Reliability has been demonstrated over short intervals using test retest item correlation; worst pain, r=0.93; usual pain, r=0.78; pain now, r=0.59. The BPI includes items that will address components of sensory pain including severity, location, chronicity and degree of relief due to therapy. The BPI also has items that address reactive pain components including depression, suffering and perceived availability of relief.

The MD Anderson Symptom Inventory (MDASI) is a flexible system for the assessment of symptoms experienced by patients with cancer (4). The MDASI consists of 13 core symptom items that are rated based on their presence and severity and 6 symptom interference items that are rated based on the level of symptom interference with function. With the MDASI, patients can rate their symptoms by completing a pencil-and-paper questionnaire or by answering items presented in an interview. The study has been validated (4) and demonstrates that reasonably small numbers of symptom items can account for the majority of symptom distress in patients with different malignancies at various stages and that these items are sensitive to expected differences in symptoms and side effects. A major advantage of the MDASI is that it is easy for most to complete. It takes most patients less than 5 minutes to rate the core symptom severity and interference items. In an outpatient setting, less than 5% of patients refused or were unwilling to complete the questionnaire. Even patients with a high level of symptom burden were able to complete the MDASI. The use of simple designations for symptom and interference items makes the MDASI very easy to understand when presented in an interview format. Many patients find the 0-10 rating system of the MDASI easy and familiar, because this type of rating is similar to the 0-10 ratings of symptom severity often used in clinical practice. In addition translation of the MDASI into other languages should be simple and straightforward.

McCormick Neurologic Function Classification Scheme (17)

Neurologic Function	Clinical Definition
1	Normal to mild focal deficit
2	Moderate deficit; significant motor or sensory loss but able to function independently

3	Moderate to severe deficit; requires assistance to ambulate
4	Severe deficit; unable to function independently or to ambulate

7.0 Criteria for Response

Pain, Symptom and Quality of Life Instruments

Frequency and duration of complete pain relief will be the primary endpoint for efficacy of the study. The validated Brief Pain Inventory (BPI), MD Anderson Symptom Inventory (MDASI), and SF-12v2 Health Survey will be used to assess changes in these indicators compared to pre-treatment baseline. Response will be determined by follow-up questionnaires. Time to maximal pain relief will be the time from the first day of irradiation until the lowest pain score for average pain after radiotherapy. The "worst pain score" from BPI will be used as the marker for treatment success or failure.

Treatment Failures

All the following are considered treatment failures:

- 1) A pain score greater than 0 that does not change within 8 weeks from start of radiation therapy.
- 2) A 2 point increase in "worst pain score" that is sustained at a higher level in the month following the first day of radiation therapy.
- 3) A pain score that drops by at least 2 points and subsequent sustained rise (on 2 successive questionnaires) of pain score by at least 2 points.

Pain Relief

- 1) Patients experiencing a decrease of 2 points in the worst pain score for 2 consecutive analysis periods will be considered to have "partial pain relief."
- 2) Complete pain relief is defined as an average pain score of 0 for 2 consecutive analysis periods.

Radiographic Assessments.

MRI of the spine will be performed according to standard of care. These data will be collected on treated lesions and will be classified as progressive defined as larger, stable defined as radiographically unchanged, or smaller.

The date of radiological progression will be recorded. Progression free survival based on time to event curves will be calculated.

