Properties of the Design Assuming Other Values of p

Quit If Evidence That $\Theta > H_0$

Prob Event	Prob Quit	Expected N	Expected N Given Quit
0.0500	0.6381	43.06	33.45
0.1000	0.9566	27.67	26.21
0.1500	0.9969	20.76	20.64
0.2000	0.9998	17.70	17.69

RESPONSE RATE

Assuming that safety concerns are met, the purpose of the trial is to estimate the response (pain relief) rate. All 60 patients entered will be used for this purpose.

Tumor control will be based on spinal MRI showing absence of progression. Actuarial and crude rates of tumor control will be calculated.

Pain relief will be assessed by items on the BPI that measure severity, location, chronicity, and degree of relief due to therapy by demographic data that will track use of narcotic and non-narcotic pain medications. For previously unirradiated patients as are in this trial, 46% of patients should demonstrate complete sensory pain relief and 90% should have some pain relief reported as a decrease in severity rating and use of pain medications and increase in the pain relief rating (Blitzer 1985).

The expected change in these indicators should occur within 1 month from the end of radiation therapy based on experience with 3 fraction SBRT on protocol ID02-446. Forty percent of patients should demonstrate complete sensory pain relief by 6 months from the end of radiation therapy as reported by the same indicators. Duration of sensory pain relief should approach a mean of 24 weeks for those patients reporting some relief and 13 weeks for those patients reporting complete relief. For patients surviving one year or more, 60% should report sustained relief based on results with standard radiation therapy.

Pain, Symptom and Quality of Life Instruments

The MD Anderson Symptom Inventory (MDASI) is a measure of symptom severity and symptom interference while the SF-12v2 Health Survey is a measure of health status. Because changes in symptom severity are usually associated with changes in health status, we are interested in assessing the relationship of symptom severity and symptom interference on health-related functional status of life using the SF12's physical and mental component scores. We will regress the MDASI with the component scores of the SF12 and examine the overlap in variability between the measures.

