The "pain worst" item from the BPI will be used as the marker for treatment success or failure. Previous studies have shown that pain severity can be categorized into mild, moderate or severe based on how pain interferes with daily functions (Serlin et al, 1995, Mendoza, et al 2004). We will calculate the proportion of patients who responded to treatment. We expect 80% of patients to respond to declare success. A responder will be defined as a patient whose "pain worst" changed from moderate or severe (5 or greater on the) to none or mild (0-4) at 1 month after enrollment. This range was selected because previous studies have shown that patients who report pain of 5 or greater on this item experience significantly greater pain-related interference with function than those with mild or no pain [Cleeland et al, 1994, Serlin et al, 1995, Wang et al, 1999].

The following are secondary considerations in determining treatment failures and pain relief.

Treatment Failures

All the following are considered treatment failures:

- 1) A pain score greater than 0 that does not change within 8 weeks from start of radiation therapy.
- 2) A 2 point increase in "worst pain score" that is sustained at a higher level in the month following the first day of radiation therapy.
- 3) A pain score that drops by at least 2 points and subsequent sustained rise (on 2 successive questionnaires) of pain score by at least 2 points.

Pain Relief

- 1) Patients experiencing a decrease of 2 points in the worst pain score for 2 consecutive analysis periods will be considered to have "partial pain relief."
- 2) Complete pain relief is defined as an average pain score of 0 for 2 consecutive analysis periods.

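### Sections 7.0 and 9.0 contradict each other on the lead pain endpoint, and the 80% success rate in Section 9.0 has no settled denominator

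*Combined protocol and SAP*

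**What the plan says.** **Lead endpoint.** Section 7.0 says: "Frequency and duration of complete pain relief will be the primary endpoint for efficacy of the study". It defines complete relief as average pain of 0 over two successive analysis periods. The same section says that the worst-pain score "from BPI will be used as the marker for treatment success or failure".

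Section 9.0, under Pain, Symptom and Quality of Life Instruments, also makes worst pain the marker. It says "We will calculate the proportion of patients who responded to treatment" and then "We expect 80% of patients to respond to declare success". A responder is a patient whose worst pain "changed from moderate or severe (5 or greater on the) to none or mild (0-4) at 1 month after enrollment". The complete-relief definition from Section 7.0 is then repeated under the sentence "The following are secondary considerations in determining treatment failures and pain relief".

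**Expected values.** Section 9.0, Response Rate, expects complete relief in 46% of patients, 40% by 6 months, with a mean duration of 13 weeks. None of these is tied to a success decision.

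**Denominator.** Response Rate gives estimation of the pain-relief rate as the purpose and adds: "All 60 patients entered will be used for this purpose". Section 3.0 lists no minimum pain score for entry.

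**Timing.** The responder rule counts from enrollment. Section 6.0 schedules questionnaires at weeks 1, 2, 3, 4 and 8 after radiation is completed. The first failure criterion concerns a score "that does not change within 8 weeks from start of radiation therapy".

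**The concern.** Each section ranks the pain endpoints, and the rankings disagree. The two endpoints differ in BPI item (average or worst), in threshold (0, or 0-4) and in duration (two periods, or one time point). A patient can meet one and not the other. In a single-arm trial, advance specification is the main protection against choosing the more favourable pain result once the data are known.

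The responder rate then raises a second problem. A patient who enters with worst pain below 5 cannot become a responder whatever the treatment does. If such patients stay in the denominator, the rate partly measures how many entrants had substantial pain. The same data could then meet 80% on one reading and miss it on the other.

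Complete relief has the reverse weakness. With no minimum pain at entry, a patient who starts at average pain 0 and stays there meets the definition without having been relieved of anything.

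**Working it through.** **1. Where the 60 comes from.** The only computed design in the plan is the safety rule in Section 9.0: looks at 15, 30, 45 and 60 patients, continuing with at most 1, 1, 2 and 2 events. An exact binomial recursion at a 1% event rate reproduces the stated stage probabilities: 0.00963 + 0.02652 + 0.00247 + 0.00809 = 0.0467. The 60 is therefore tied to safety. No sample size, error rate or power is given for any pain endpoint.

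**2. Can the 80% bar belong to complete relief?** 80% of 60 is 0.80 × 60 = 48.
- At the plan's 46%: P(Bin(60, 0.46) ≥ 48) ≈ 7 × 10⁻⁸.
- At the plan's 40%: P(Bin(60, 0.40) ≥ 48) ≈ 3 × 10⁻¹⁰.

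The bar makes sense only for the worst-pain rule.

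**3. Responder rate over all 60.** Let m be the number with baseline worst pain of 5 or more. The documents do not give m, so the values below are assumptions. The highest attainable rate is m/60, and 80% requires 48 responders among the m.

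| m (assumed) | Highest rate over 60 | Response needed among the m |
|---|---|---|
| 30 | 50.0% | not attainable |
| 40 | 66.7% | not attainable |
| 50 | 83.3% | 48/50 = 96.0% |
| 55 | 91.7% | 48/55 = 87.3% |

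Below m = 48 the bar is out of reach.

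**4. Chance of meeting 80% if true response among the m is 80%.**
- m = 50, over all 60: P(Bin(50, 0.8) ≥ 48) = 0.00129, or 0.13%.
- m = 50, over those 50 (40 needed): P(Bin(50, 0.8) ≥ 40) = 0.584.
- m = 55, over all 60: P(Bin(55, 0.8) ≥ 48) = 0.116.
- m = 60, where the readings coincide: P(Bin(60, 0.8) ≥ 48) = 0.576.

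**5. Precision at an observed 80% (Clopper-Pearson, 95%).** 48/60: 67.7-89.2%. 32/40: 64.4-90.9%. 24/30: 61.4-92.3%.

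**6. Timing.** The plan states no interval from enrollment to treatment and no visit window. If treatment falls 0 to 1 week after enrollment (assumption), one month after enrollment lies at or near the week 3 or week 4 questionnaire. A longer delay moves it to an earlier one.

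**The case against.** The strongest defence is that the trial sets out to estimate a pain-relief rate. There is no null rate, error level or power for pain, and the 80% sentence is worded partly as an expectation. The responder definition speaks of change from moderate or severe pain, so it is natural to count only patients who start there; on that reading the loss in steps 3 and 4 disappears. Much of this stands. The 80% should not be treated as a formal test, and the 0.13% against 58.4% contrast is a scenario. But the sentence does link 80% to declaring success, and even a pure estimate needs a defined population and time point. The only explicit statement about which patients are used for the pain-relief rate points to all 60.

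Three stronger readings are tempting, and the documents do not support them:
- A reader might infer that the plan never says which pain endpoint leads. It does, in both sections; the answers conflict.
- A reader might infer that the enrollment clock matches none of the questionnaires. With early treatment it falls at or near week 3 or 4. The gap is only that the deciding form is not fixed.
- A reader might infer that the 80% target is unattainable. That requires both the all-60 reading and fewer than 48 patients starting at 5 or more, and the baseline share is not stated.

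**Conclusion.** The contradiction is established from the text alone: complete pain relief is primary in Section 7.0 and a secondary consideration in Section 9.0, where success rests on a different endpoint. The endpoint called primary has expected values but no success threshold. This affects what the trial can claim about pain and should be resolved before any pain result is analysed.

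The denominator ambiguity is also real, but its size is conditional. It is nil if the rate is taken among patients starting at 5 or more. On the all-60 reading it can lower the chance of meeting 80% from 58.4% to 0.13% (50 such patients, true response 80%), or remove it altogether with fewer than 48. With 55 such patients the chance is 11.6%. The timing mismatch is minor, and no effect on the result has been shown for it.

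**What to change.** 1. Name one primary pain endpoint in identical words in Sections 7.0 and 9.0, and label the other secondary. The worst-pain responder is the natural candidate because only it has a success threshold, but the choice is the sponsor's. If complete relief is chosen, state its benchmark from Response Rate and say that the 80% bar does not apply to it.
2. Assess the responder rule at the scheduled 4-week post-radiation BPI, among patients with baseline worst pain of 5 or more. Count a missing 4-week score as non-response. Exclude patients without a baseline score and report their number.
3. Compute complete relief among patients with baseline average pain above 0.
4. Present 80% as a benchmark on the observed proportion, with its exact 95% interval.

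The cost is wording only, since the baseline and 4-week BPI are already collected. The price is a smaller denominator and a wider interval: at an observed 80%, 61.4-92.3% with 30 patients against 67.7-89.2% with 60.
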